### 6.1.1.2. Investigator Determination of Clinical and Microbiologic Response at EOIVT

As described in [Section 6.1.1.1](#), global response will be derived programmatically based on the investigator's assessment of clinical and microbiologic response.

Definitions of clinical and microbiologic response, which investigators are asked to follow, are listed below:

#### **Clinical Response**

**Cure:** Resolution of sign and symptoms attributed to *Candida* infection; no additional systemic or oral antifungal treatment required to complete the course of therapy.

**Improvement:** Significant, but incomplete resolution of signs and symptoms of the *Candida* infection; no additional systemic or oral antifungal treatment required to complete the course of therapy.

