### **5.2.5. Compliance**

It is expected that the majority of the subjects will receive study drug in the hospital setting. In this case, compliance with IV and oral therapy administered during hospitalization will be assessed by the Study Monitor during site visits, and by the sponsor upon review of the study data at the end of the study.

Subjects who are switched to oral treatment and discharged from the hospital will be provided with a known quantity of oral study medication for continued therapy in the outpatient setting. Appropriate drug accountability measures should be implemented to appropriately evaluate compliance. Subjects should also be interviewed regarding adherence to treatment.

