#### 6.4. End of Oral Therapy (if applicable)

The following assessments will be performed on the last day (or within 24 hours of the last day) of oral anidulafungin treatment:

- Targeted physical examination (including vital signs);
- Assess signs and symptoms of *Candida* infection;
- Fundoscopic examination, only if the baseline fundoscopic examination was abnormal;
- Blood cultures (for subjects with microbiologically confirmed ICC);
- Specimen culture (from other normally sterile sites as clinically indicated);
- CBC with differential (same as in screening);
- Serum chemistry (same as in screening);
- Echocardiogram, either transesophageal (preferred) or transthoracic (to be performed only in subjects with *Candida* endocarditis) (**not applicable to Korean and Portuguese investigator sites**);
- Magnetic Resonance Imaging (MRI) study (to be performed only in subjects with *Candida* osteomyelitis) (**not applicable to Korean and Portuguese investigator sites**);
- Urine or serum pregnancy test (for females of childbearing potential);
- Evaluation of clinical and microbiologic response (See [Section 7.4](#)) (to be performed only in subjects with microbiologically confirmed ICC).
- Record adverse events and concomitant medications.

**\*\* Please Note \*\*** The EOT is defined as either (1) the end of IV anidulafungin if subject is not switched to oral fluconazole, or (2) the end of the oral fluconazole if subject is switched from IV anidulafungin to oral fluconazole.

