#### **7.4. Clinical and Microbiologic Response Assessment**

##### **7.4.1. Subjects with Invasive Candidiasis/Candidemia (Except for Subjects with *Candida* Endocarditis or *Candida* Osteomyelitis)**

###### **7.4.1.1. Clinical Response at End of IV Treatment (EOIVT) and End of Treatment (EOT)**

Clinical response is defined as follows:

- **Cure**: Resolution of signs and symptoms attributed to *Candida* infection; no additional systemic antifungal;
- **Improvement**: Significant, but incomplete resolution of signs and symptoms of the *Candida* infection; no additional systemic antifungal;
- **Failure**: No significant improvement in signs and symptoms, or death due to the *Candida* infection. Subjects must have received at least 3 doses of study medication to be classified as a failure;
- **Indeterminate**: Evaluation cannot be made due to withdrawal from the study prior to assessment of cure or failure. Subjects who receive fewer than 3 doses of study medication will be assigned a clinical efficacy response of indeterminate.

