## **9. DATA ANALYSIS/STATISTICAL METHODS**

Detailed methodology for summary and statistical analyses of the data collected in this trial will be documented in a Statistical Analysis Plan, which will be dated and maintained by the sponsor. This document may modify the plans outlined in the protocol; however, any major modifications of the primary endpoint definition and/or its analysis will also be reflected in a protocol amendment.

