**Success:**

- **Cure:** Resolution of signs and symptoms attributed to *Candida* infection; no additional systemic antifungal; ~~treatment, or oral fluconazole required to complete the course of therapy;~~
- **Improvement:** Significant, but incomplete resolution of signs and symptoms of the *Candida* infection; no additional systemic antifungal ~~treatment, or additional oral fluconazole required;~~
- Failure:
- **Failure: Failure:** No significant improvement in signs and symptoms, or death due to the *Candida* infection. Subjects must have received at least 3 doses of study medication to be classified as a failure;
- Indeterminate:
- **Indeterminate:** ~~Indeterminate:~~ Evaluation cannot be made due to withdrawal from the study prior to assessment of cure or failure. Subjects who receive fewer than 3 doses of study medication will be assigned a clinical efficacy response of indeterminate.

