## 1. AMENDMENTS FROM PREVIOUS VERSION(S)

This SAP is an amendment of version 1.0.

The analysis of the global response endpoint has been clarified. Other minor changes have been made to bring the SAP in agreement with Protocol Amendment 3.

This SAP is an amendment of version 2.0. The changes have been made to bring the SAP in agreement with protocol Amendment 4. The primary changes for Protocol Amendment 4 allow enrolment of subjects with *Candida* endocarditis and *Candida* osteomyelitis.

This SAP is an amendment of version 3.0. The changes have been made to tighten up the definition of the global response endpoint.

This SAP is an amendment of version 4.0. The changes have been made to conduct additional analysis with subjects who completed study treatment.

This SAP is an amendment of version 5.0. This amendment reflects the changes that were made in protocol amendments 8 and 9, which include expansion of enrolment criteria to include infants (aged 1 month - < 2 years) who do not have microbiologically confirmed *Candida* but who are at high risk of candidiasis, analysis of pharmacokinetic parameters of polysorbate 80, and addition of an interim analysis.

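### For Candida endocarditis and osteomyelitis, the SAP puts an antifungal condition on 'improvement' that the protocol does not set, so the two documents can classify the same child differently.

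*SAP*

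**What the plan says.** Protocol 7.4 defines clinical response separately for two groups.

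- **General group (7.4.1.1, 7.4.1.3).** Both cure and improvement carry the condition "no additional systemic antifungal".
- **Endocarditis and osteomyelitis (7.4.2.1, 7.4.2.3).** Only cure requires that no additional or ongoing systemic antifungal is given. Improvement is defined by significant but incomplete resolution, with no antifungal condition.

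The SAP has one set of definitions for all subjects. In 6.1.1.2 (extended to EOT by 6.1.2) and in 6.1.3, cure and improvement both require "no additional systemic or oral antifungal treatment required to complete the course of therapy". Section 6.1.3 makes its version the programmatic definition at Weeks 2 and 6. Its note says that further antifungal therapy not clearly recorded as prophylactic is taken as treatment of continued infection and counts as clinical failure. A Week 2 failure is carried forward.

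SAP 6.1.4 has a separate algorithm. In the follow-up period it imputes failure only when the antifungal was taken for lack of efficacy, as judged by the clinical team.

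SAP 2.1, like Protocol Section 3, foresees that some children with these two diagnoses will need treatment beyond the 49-day maximum. That treatment lies outside the trial, and the children return for both follow-up visits.

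**The concern.** Planned continuation of therapy is foreseen for exactly the children whose protocol definition of improvement ignores it, and the SAP definition penalises it. The two documents can therefore give different global responses for the same child on the same data, and the SAP errs towards fewer successes. The SAP also gives two answers of its own at follow-up, one in the 6.1.3 note and another in 6.1.4.

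The affected outputs are the global response rates, which are among the interim tables in SAP Appendix 2. The sensitivity analysis in SAP 8.2.2 drops only indeterminate and missing responses, so a child deemed a clinical failure at Week 2 would stay a failure in it. The primary safety objective is not touched.

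**Working it through.** No figure in the plan depends on this point: Protocol 9.4 reports no sample size calculation and SAP 4.1 plans no test. The check is therefore a comparison of texts, followed by the size of one reclassification.

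**Test case.** A child with endocarditis or osteomyelitis has significant but incomplete resolution and eradication or presumed eradication. The child continues antifungal treatment after the last day of study drug, for a reason other than lack of efficacy.

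| Visit | Protocol 7.4.2 with 7.3 | SAP definitions | SAP 6.1.4 |
|---|---|---|---|
| EOT | Improvement, so success | As worded, neither cure nor improvement (6.1.1.2 via 6.1.2), so not a success | No imputation for therapy that starts after EOT |
| Week 2 | Improvement, so success | Not improvement; the 6.1.3 note makes it clinical failure | No failure, because not for lack of efficacy |
| Week 6 | Improvement, so success | Same as Week 2, and a Week 2 failure carries forward | No failure |

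The protocol and the SAP definitions disagree on every row, and the last two columns disagree at both follow-up visits.

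**Size per child.** Denominators are the planned 60 evaluable subjects, the 20 ± 2 per age stratum, and the two interim strata together (2 × 20 = 40). The shift is 100/n points, whatever the true rate:

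- n = 60: 100/60 = 1.7
- n = 40: 100/40 = 2.5
- n = 20: 100/20 = 5.0 (100/22 = 4.5 and 100/18 = 5.6 at the ends of the range)

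**Illustration.** Assume a success rate near 75%, anchored on the 75.6% in the adult trial (Protocol 1.3.2), and one or two children reclassified. Both are assumptions. Intervals are exact Clopper-Pearson, as in SAP 8.1.1.

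- Of 60: 45/60 = 75.0% (95% CI 62.1 to 85.3) becomes 44/60 = 73.3% (60.3 to 83.9) or 43/60 = 71.7% (58.6 to 82.5).
- Of 20: 15/20 = 75% (50.9 to 91.3) becomes 14/20 = 70% (45.7 to 88.1) or 13/20 = 65% (40.8 to 84.6).

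For assumed base rates from 60% to 90%, interval half-widths are about 8 to 13 points at n = 60 and 15 to 22 at n = 20. One or two children shift the estimate by less than that.

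**The case against.** **The stricter rule may be deliberate.** Protocol Section 9 says of the SAP that "This document may modify the plans outlined in the protocol", and requires an amendment only for major changes to the primary endpoint. SAP Section 1 records, after the version aligned with Amendment 4, a version of which it says "The changes have been made to tighten up the definition of the global response endpoint". That is a fair explanation and cannot be excluded. But no passage says that the 7.4.2 definitions were set aside. The preceding entry gives the aim "The changes have been made to bring the SAP in agreement with protocol Amendment 4", and Amendment 4 is the one that added those definitions. If the departure is intended, it needs to be stated.

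**Section 6.1.4 might rescue these children.** It is the explicit follow-up algorithm and would not fail them. However, it sets failures in addition to the clinical response, and nothing says it overrides the 6.1.3 note. What stands is that the SAP is unsettled, so failure is not certain.

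**A reader might infer that every child stepped down to oral fluconazole fails at EOIVT, and that carry-forward then fixes all four visits.** The documents do not support this.

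- An improved child does not meet the SAP definition of failure.
- The deeming note concerns therapy after EOT, and EOT for a switched child is "the end of the oral fluconazole if subject is switched from IV anidulafungin to oral fluconazole".
- Section 6.1.4 covers concomitant drugs identified by the clinical team, and imputes failure only to visits after they were taken.
- Protocol 5.2.5 says discharged children "will be provided with a known quantity of oral study medication", SAP 5.3.1 accepts IV plus oral treatment, and SAP 5.5.2 counts a switch as a deviation only if the criteria were not met.
- Protocol 7.4.1.1 has no express step-down exemption either.

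What remains is that neither 6.1.1.2 nor 6.1.4 says this outright, while Protocol 5.2.1 lists fluconazole separately from the study drug.

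**A reader might also take the SAP phrase as a remnant** of the clause on "oral fluconazole required to complete the course of therapy" that Amendment 4 struck from the protocol. That clause named fluconazole and the SAP phrase does not. The later tightening could equally be its source, so its origin cannot be established.

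**Conclusion.** The conflict over endocarditis and osteomyelitis is real and lies between current texts. It should be settled, but its expected effect is small. The endpoint is secondary and descriptive. The documents give no expected number of these children; exclusions 14 and 15 and the Korean and Portuguese restrictions make it probably very small, and it could be zero. One child is worth 1.7 points overall and 5.0 in a stratum of 20, always downward, provided the planned denominators are reached and the SAP definitions are applied as worded.

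The step-down wording is a minor clarification, not a second defect.

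**What to change.** Before the interim tables are produced:

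1. Reconcile SAP 6.1.1.2, 6.1.2 and 6.1.3, including the 6.1.3 note, with Protocol 7.4.2 by using the protocol's response definitions for endocarditis and osteomyelitis. Keep the lack-of-efficacy imputation in 6.1.4, so that the note and the algorithm agree. If one stricter rule is intended, state it as a departure from 7.4.2 and give the reason.
2. State how a fully resolved child still on continued therapy is classified. As worded, 7.4.2 fits neither cure, because therapy is ongoing, nor improvement, because resolution is complete. The choice also affects the cure-based rate in SAP 6.1.5.
3. List every subject whose category differs between the two definitions.
4. As a clarification, add one sentence to SAP 6.1.1.2 and 6.1.4: protocol-permitted oral fluconazole step-down, through EOT, is study treatment and is neither additional nor concomitant antifungal therapy for response classification.

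The cost is SAP wording and derivation code, with no new data. The downside is that, for these few children, the result rests more on the investigator's judgement of improvement, and a success may be counted before therapy ends.

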#### ***Important Notes:***

- Initiating or resuming oral antifungal therapy following EOT for prophylactic purposes is permitted, and does not reflect a requirement for additional systemic antifungal therapy for treatment purposes, and therefore does not constitute treatment failure. (Note: It must be clear in the project database that administration of additional antifungal therapy is for prophylactic purposes, otherwise it will be deemed as being administered for treatment of continued infection, in which case study drug treatment will be considered clinical failure.)
- Administration of non-absorbable antifungal agent is not considered systemic antifungal treatment in the context of this study.

**Failure:** No significant improvement in signs and symptoms, or death due to the *Candida* infection. Subjects must have received at least 3 doses of study medication to be classified as a failure.

**Indeterminate:** Evaluation cannot be made due to withdrawal from the study prior to assessment of cure or failure. Subjects who receive fewer than 3 doses of study medication will be assigned as a clinical efficacy response of indeterminate.

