#### 6.1.1. Global Response at the End of IV Treatment (EOIVT)

##### 6.1.1.1. Global Response Determination at EOIVT

Global response at EOIVT is based on assessment of clinical and microbiological response provided by the investigator at this time point, and will be programmatically determined as follows:

**Success:** A patient will be categorized as having successful response if there is a clinical response of cure or improvement and microbiological eradication or presumed eradication.

**Failure:** A patient will be categorized as having an unsuccessful response if there is a clinical response of failure and/or unsuccessful microbiological response (persistence or new infection at FU or relapse at FU).

**Indeterminate:** A patient will be categorized as indeterminate if there is a clinical response of indeterminate and /or microbiological response of indeterminate and neither clinical response is a failure nor unsuccessful microbiological response (persistence or new infection or relapse).

A global response determination of failure at EOIVT will be carried forward programmatically to all subsequent visits.

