#### **Microbiological Response**

**Eradication or presumed eradication:** Baseline pathogen not isolated from original site culture(s), or culture data are not available for a subject with successful clinical outcome.

**Persistence (documented or presumed):** Any baseline *Candida* sp. is present in repeat cultures, or culture data are not available for subject with a clinical outcome of failure.

**Indeterminate:** Culture data are not available for a subject with a clinical outcome of indeterminate.

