## 7. HANDLING OF MISSING VALUES

For global response, missing values are treated as failures. Sensitivity analyses will also be performed in which subjects with missing values for global response are excluded from the analysis.

For the analysis of safety endpoints, the sponsor data standard rules for imputation will be applied.

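### Death on therapy from a cause other than Candida has no response category, so a child who died can be counted as a global success at EOIVT or EOT

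*SAP*

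**What the plan says.** SAP 6.1.1.2 defines clinical failure as "No significant improvement in signs and symptoms, or death due to the" *Candida* infection, and adds: "Subjects must have received at least 3 doses of study medication to be classified as a failure". Indeterminate has two routes. One, worded the same way in protocol 7.4.1.1 and the SAP, is: "Evaluation cannot be made due to withdrawal from the study prior to assessment of cure or failure". The other is low exposure: "Subjects who receive fewer than 3 doses of study medication will be assigned as a clinical efficacy response of indeterminate".

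Improvement in the SAP needs significant but partial resolution of signs and symptoms, with "no additional systemic or oral antifungal treatment required to complete the course of therapy". The protocol's clause in 7.4.1.1 is shorter and does not mention completing the course. For endocarditis and osteomyelitis, improvement in protocol 7.4.2.1 has no antifungal clause at all.

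Microbiological eradication is presumed when "culture data are not available for a subject with successful clinical outcome". Global success is assigned "if there is a clinical response of cure or improvement and microbiological eradication or presumed eradication" (SAP 6.1.1.1), and SAP 6.1.2 applies the same definitions at EOT.

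SAP 7 adds: "For global response, missing values are treated as failures". The sensitivity analysis in SAP 8.2.2 drops indeterminate and missing responses. All-cause mortality is reported separately (SAP 6.1.5.3).

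**The concern.** The response categories deal with Candida deaths, withdrawals and very short exposure. They do not deal with a child who dies on treatment of something else. The protocol expects such competing events: section 8.5.1 lists progression of malignancy, aspergillosis and bacterial infection as serious events anticipated in this population.

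Without a rule, the classification of one clinical event depends on how the site completes the form and on an open-label investigator's view of the cause of death. Neither document describes independent adjudication of response or of cause of death. The SAP does override the investigator's rating elsewhere: section 6.1.4 sets global response to failure after two or more days of another antifungal on treatment, whatever the reason. There is no matching override for death.

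At stake is the meaning of the EOIVT and EOT success rates in the MITT set, which could include children who had died by the time point.

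**Working it through.** The plan states no figure on this point to reproduce. The check is a trace through the definitions, followed by simple proportions.

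**Trace.** Take a child in the MITT set with at least 3 doses, who dies on therapy of a cause other than Candida after the Candida signs had improved.

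1. Clinical failure does not apply as written: there was improvement, and the death was not due to Candida. Indeterminate does not name death. Improvement does not require survival.
2. If repeat cultures were negative, the microbiological response is eradication. If none were taken, it is presumed eradication, because the clinical outcome is a success.
3. Improvement plus eradication, documented or presumed, is global success.

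The recorded rating decides the result:

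- Investigator records improvement: **success**, in both the main and the sensitivity analysis.
- No response recorded: missing, so **failure** in the main analysis, and dropped from the sensitivity analysis.
- Death handled as withdrawal before assessment: **indeterminate**, not a success, and dropped from the sensitivity analysis.

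With fewer than 3 doses the child is indeterminate by rule.

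**Which time point.** Protocol 6.3 places the EOIVT assessment on the final IV day or within a day of it. Protocol 6.4 makes EOT the end of IV therapy when there is no switch. A death on IV therapy therefore affects EOIVT and EOT together. A child who dies on oral fluconazole was alive at EOIVT, so that rating is legitimate and only EOT is affected.

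**Size per child.** Inputs: about 60 evaluable children (SAP 2.1.2) and 20 ± 2 per age stratum (SAP 3.1).

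- Overall: 1/60 = 1.7 points.
- Stratum: 1/22 = 4.5 points to 1/18 = 5.6 points.

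**Illustration.** Assume 45 of 60 are counted as successes, 75.0% (exact 95% CI 62.1 to 85.3), and that k of the 45 are such deaths. The base is chosen near the adult 75.6% in protocol 1.3.2. Both it and k are assumptions.

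- k = 1 reclassified as failure: 44/60 = 73.3% (60.3 to 83.9).
- k = 3 reclassified as failure: 42/60 = 70.0% (56.8 to 81.2).
- k = 3 classed as indeterminate and excluded: 42/57 = 73.7%.
- One stratum of 20 at 15/20 = 75.0%, k = 1 as failure: 14/20 = 70.0%.

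**The case against.** The strongest reply is that success is not the default. It needs an investigator's rating of cure or improvement, and a child who dies before the assessment may have none; SAP 7 then makes that child a failure. Death before assessment can also be read as a form of withdrawal, which gives indeterminate. It is doubtful that a child who dies mid-course satisfies the SAP clause about completing the course. Protocol 7.2 lists sepsis and organ dysfunction among signs of Candida infection, so some dying children would not fit significant improvement.

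All of this stands, and it narrows the route to success without closing it. The withdrawal and course-completion readings are interpretations that the text does not state. The protocol's shorter clause is met on its face. The missing-data rule helps only when the form is blank.

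Global response is also secondary and descriptive, with all-cause mortality, causes of death and Kaplan-Meier curves reported alongside. That limits the consequence. Those outputs still do not show how many children who died are inside the success count.

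Finally, counting only Candida deaths as clinical failure is the protocol's own definition, and failure for any-cause death is one choice among two. In the main analysis both choices are non-success, so they differ only where indeterminate responses are excluded. A blanket failure rule would collide with the 3-dose rule; the fix has to respect that.

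**Conclusion.** The gap is real and worth closing before the final analysis. Other-cause death on therapy belongs to no response category, and the same event can be a success, a failure or indeterminate. The sensitivity analysis does not expose the problem, because a child rated improved is neither missing nor indeterminate.

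A reader might infer that every improving child who dies of another cause automatically meets the success definition. The documents do not support that: a recorded rating of cure or improvement and at least 3 doses are needed. A reader might also infer that a death on oral therapy corrupts the EOIVT result; it does not.

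Nor can a total effect be derived from the mortality figures in the protocol. The adult 22.9% includes deaths shortly after that study, the paediatric figure approaching 30% is given without timing or cause, and neither document gives the share of deaths not due to Candida or the share of those children rated improved. The supportable size is 1.7 points overall and about 4.5 to 5.6 points in a stratum for each affected child, assuming the planned numbers are reached.

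**What to change.** Add to SAP 6.1.1.1 and 6.1.2:

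- A child who died of any cause on or before the EOIVT or EOT assessment cannot be a global success at that or any later visit.
- Such a child is set to failure in the main analysis if at least 3 doses were received, and stays indeterminate (non-success) under the existing rule if fewer.
- An EOIVT response validly assessed before a later death on oral therapy is unchanged.

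Report the number of other-cause deaths among the non-successes at each time point, with a supportive analysis that classes them as indeterminate.

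The cost is a short SAP addition and some programming from death dates already collected (SAP 6.1.5.4). Protocol section 9 lets the SAP modify planned analyses and requires a protocol amendment only for major changes to the primary endpoint, which this is not. The downside is that the stated success rate may be slightly lower.
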